List of Figures within the Protocol

Figure 1: Sample of ClearPlay© Interface	17
Figure 2: Study Design.....	20

List of Tables within the Protocol

Table 1: Study Objectives and Endpoints	21
Table 2: Therapeutic Interventions.....	27
Table 3: Categories of Adverse Events	31
Table 4: Order of Assessments Post Randomization	41
Table 5: Schedule of Events	42

LIST OF ABBREVIATIONS

Abbreviation	Definition
ADHD	attention deficit hyperactivity disorder
AE	adverse event
ASI	Anxiety Sensitivity Index
BAI	Beck Anxiety Inventory
BCBT	Buffalo Concussion Bicycle Test
BCTT	Buffalo Concussion Treadmill Test
BESS	Balance Error Scoring System
BP	blood pressure
BSI	Brief Symptom Inventory
CAARS	Conners' Adult Attention Deficit Hyperactivity Disorder Rating Scale
CES-D	Center for Epidemiologic Studies - Depression Scale
CT	computed tomography
DNA	deoxyribonucleic acid
eCRF	electronic case report form
GCP	Good Clinical Practice
HR	heart rate
HREC	Human Research Ethics Committee
HRV	heart rate variability
ICH	International Council for Harmonisation of Technical Requirements for Pharmaceuticals for Human Use
MedDRA	Medical Dictionary for Regulatory Activities
MRI	magnetic resonance imaging
mTBI	mild traumatic brain injury
PCSS	Post-Concussion Symptom Scale
PICF	patient information and consent form
PPCS	persistent post-concussive symptoms
RNA	ribonucleic acid
SAE	serious adverse event
SAP	statistical analysis plan
SNP	single nucleotide polymorphisms
SSRI	selective serotonin reuptake inhibitors
SUSAR	suspected unexpected serious adverse reactions
TBI	traumatic brain injury
TCA	tricyclic antidepressants

Abbreviation	Definition
VOMS	Vestibular-Oculomotor Screening

SYNOPSIS

Protocol Number:	ExACTT-2	
Title:	A Therapeutic Intervention, Open Label Study to Compare the Efficacy and Safety of Graded Exercise Compared to Passive Stretching in Subjects Who Have Sustained a Mild Traumatic Brain Injury	
Therapeutic Intervention:	The therapeutic intervention (graded exercise) to be used in this study is delivered through the ClearPlay© mobile application. ClearPlay© provides the subject with a graded exercise program or passive stretching program, which is used in conjunction with a wrist-worn heart rate monitoring device (Waveband®).	
Study Centre:	Multiple sites in Australia	
Development Phase:	Phase 2	
Objectives and Endpoints:	Objectives	Endpoints
	Primary Objectives	Primary Endpoints
	To compare the effects of graded exercise to passive stretching using ClearPlay© on symptomatic recovery rate following mTBI.	
 • Within-subject analysis of change in symptoms over time using the PCSS, comparing short-term ‘survival rates’ between graded exercise and stretching using Kaplan-Meier analyses for days since concussion.
	Secondary Objectives	Secondary Endpoints
	To compare the safety and tolerability of graded exercise to passive stretching in patients following mTBI.	
 • Adverse events reported from Day 1 through Day 56, including those identified during exercise or passive stretching during the 20 minutes of daily therapy.
To compare symptom resolution following graded exercise compared to passive stretching using ClearPlay© following mTBI.	
 • Within subject analysis of change in the number of subjects who are symptom free at 8 weeks between the 2 groups. Symptom free is defined by subjects having 3 consecutive days of PCSS scores lower than pre-concussion. 
Note: This objective is similar to the primary one, with the primary endpoint being recovery (binary outcome) vs. symptom resolution (continuous variable).
 
 • Determine differences in symptomatic recovery based on gender, baseline scores on the PCSS, baseline athletic fitness (Godin leisure-time exercise questionnaire), the history of injury, a history of migraine, as well as the presence of pre-morbid anxiety. 	
To compare the effects of graded exercise to passive stretching using ClearPlay© on physiologic recovery rate following mTBI.	
 • Within subject analysis of normalization of physiologic measurements obtained during the BCBT comparing data collected on entry to the study on Day 0 vs. follow up on Day 56 including: 
 - Beat to beat BP; • Determine differences in physiologic recovery based on gender, baseline scores on the PCSS, baseline athletic fitness (Godin 	

		leisure-time exercise questionnaire), the history of injury, a history of migraine, as well as the presence of pre-morbid anxiety (BAI; BSI-18; ASI).
	To compare the effects of graded exercise to passive stretching using ClearPlay© on accelerating symptomatic vs. physiologic recovery rate following mTBI.	
 • Combined analysis of data from the two secondary analyses outlined above to confirm or refute a significant correlation between symptom resolution (defined by subjects having 3 consecutive days of PCSS scores lower than pre-concussion) and physiologic measurements obtained during the BCBT comparing data obtained on entry to the study on Day 0 vs. follow up on Day 56 including: 
 - Beat to beat BP;
	To develop a composite physiologic metric to predict the magnitude and duration of ongoing post-concussive symptoms.	
 • Develop predictive modeling algorithms to establish a composite physiologic metric predictive of subjects becoming symptom free (as defined by subjects having 3 consecutive days of PCSS scores lower than pre-concussion) using data derived from baseline physiologic testing with: 
 - BCBT - Ice bucket testing - ClearPlay© testing
	To develop a composite neuropsychologic metric to predict the magnitude and duration of ongoing post-concussive symptoms.	
 • Develop predictive modeling algorithms to establish a composite neuropsychologic metric predictive of subjects becoming symptom free (as defined by subjects having 3 consecutive days of PCSS scores lower than pre-concussion) using data derived from baseline neuropsychologic testing with the following instruments: 
 - Attention (CAARS) - Depression (CES-D) - Anxiety (BAI; BSI-18; ASI).
	To develop a composite blood-based OR saliva biomarker metric to predict the magnitude and duration of ongoing post-concussive symptoms.	
 • Analysis of biomarkers at baseline testing including: 
 - Structural proteins [t-tau, NF-L, GFAP and UCH-L1] - Inflammatory cytokines [IL-6, IL-10 and TNFα] - SNPs [APO-E4, BDNF, and NFkB]
	To validate the performance of ClearHeart© against ice bucket testing.	
 • Bland-Altman plots will be used to evaluate the agreement between HR measured by ClearHeart© and ice bucket testing. • Bland-Altman plots will be used to evaluate the agreement between BP measured by ClearHeart© and ice bucket testing.
	To validate the performance of	
 • Correlations will be used to assess the association between results obtained through ClearNeck© testing and those obtained

	
ClearNeck© against examination of the neck
 
during the neurologic examination for neck range of motion and tenderness.

	
Abbreviations: ASI = Anxiety Sensitivity Index, BAI = Beck Anxiety Inventory, BCBT = Buffalo Concussion Bicycle Test, BESS = Balance Error Scoring System,; BP=blood pressure, BSI = Brief Symptom Inventory, CAARS = Conners' Adult Attention Deficit Hyperactivity Disorder Rating Scale, CES-D = Center for Epidemiologic Studies - Depression Scale,HRV = Heart Rate Variability, TBI = mild traumatic brain injury; PCSS = Post-Concussive Symptom Scale, SNP = single nucleotide polymorphisms.

Study Design:	
This study is a Phase 2, open label study of a therapeutic intervention (graded exercise) compared to a reference therapy (passive stretching) in patients who have sustained mTBI. Subjects will be randomly assigned with a ratio of 1:1 to complete either graded exercise or passive stretching using a parallel group design.

Recruitment	
The study sites will have well-established concussion research programs and referral populations.

Administration of Therapeutic Intervention:	
The therapeutic intervention is either 20 minutes daily of graded exercise or 20 minutes daily of passive stretching, according to the randomization schedule, from Day 1 to Day 56.

Inclusion Criteria:	
To be eligible for study entry, subjects must satisfy all of the following criteria:
 
 1. Male or female subjects aged ≥ 14 to ≤ 45, able and willing to provide informed consent (≥ 18 years), or informed consent is obtained by the parent or legal guardian for minor subjects, with the minor providing age appropriate assent, according to local law and regulations; 2. Subject is fluent in English, able to understand and agree to comply with protocol requirements, able to complete all assessments, and able to be; 3. Subject has a history of recent concussion as diagnosed by a health care professional within 3 to 14 days of enrolment; 
Note: Concussion is defined as a head injury/blow to the head resulting in any of the following 3 signs and/or new symptoms: (1) Amnesia for less than 24 hours; (2) Loss of consciousness for less than 30 minutes; (3) Glasgow Coma Scale score ≥ 13; (4) Dazed and Confused/bell rung; with at least 1 new symptom or augmentation of a previous symptom on the Post-Concussion Symptom Scale (PCSS) as compared with baseline at the time of enrolment, including: headaches, dizziness, fatigue, irritability, insomnia, difficulty concentrating, and/or memory difficulties; (5) The composite symptom score on the PCSS must be at least 3 points higher post-concussion than pre-concussion.
 
 4. Subject has daily access to the internet.
Exclusion Criteria:	
Subjects will be excluded from the study if any of the following criteria are applicable:
 
 1. History of prior head injury as defined by: 
 • An injury/blow to the head within 12 months prior to screening with any associated residual symptoms; • An injury/blow to the head within 3 months prior to screening diagnosed as a concussion; • An injury/blow to the head within 3 months prior to screening with any of the following symptoms: amnesia, loss of consciousness, dazed and confused/bell rung; 2. Evidence of blood or micro-hemorrhages on prior or current computed tomography scan or magnetic resonance imaging scan if obtained; 3. Diagnosis of a neurological condition including the following: stroke, multiple sclerosis, epilepsy, brain tumor/cancer, encephalitis, dementia, movement disorder, or spontaneous nystagmus;

	
 4. Psychiatric history with any of the following: 
 • History of psychiatric hospitalization, history of legal trouble for violence; • Requires psychotropic medication other than (1) stable dose of a selective serotonin reuptake inhibitors (SSRI) medication, or (2) stable dose of a tricyclic antidepressants (TCA) medication; • Prior diagnosis of psychotic disorder, bipolar disorder, eating disorder, substance (incl. alcohol) abuse disorder; 5. Current use of beta blockers (an anti-hypertensive medication); 6. History of drug or alcohol dependency or abuse within a year before Screening, by self-report; 7. Two or more of the following cardiovascular risk factors: 
 • Prior diagnosis of, or currently taking medication for cardiovascular, metabolic or pulmonary conditions; • Family history of myocardial infarction, coronary revascularization or sudden death before 55 years; • Diagnosis of hypertension; • Diagnosis of hyperlipidemia; • Subjects with peripheral circulatory disorders; 8. Subjects who are unable or unwilling to exercise for health or personal reasons; 9. Subjects who have musculoskeletal injuries which could make exercise difficult or painful.
Sample Size:	At least 400 subjects aged 14 to 45 will be enrolled in this study at up to 5 study sites.
Analysis:	
No interim analysis is planned for this study.
 
In general, data will be summarized using descriptive statistics (number of non-missing observations, mean, median, standard deviation, minimum and maximum) or frequency counts and percentages, as appropriate to the type of data.
 
Adverse events and medical history will be coded with Medical Dictionary for Regulatory Activities (MedDRA, the latest version) and concomitant medications are coded with World Health Organization Drug coding Dictionary (latest version).
 
For all subjects, daily reported PCSS scores collected from ClearPlay© mobile application will be utilized to determine the resolution of symptoms. The resolution of symptoms is defined as a symptom-severity score of less than each subject's pre-injury PCSS score for 3 consecutive days. To assess differences in the probability of symptom resolution between graded exercise and passive stretching during the 8 weeks of therapy, both unadjusted and adjusted logistic regression models will be used. The primary outcome of the study will be to confirm or refute the superiority of sub-threshold aerobic exercise versus passive stretching to result in resolution of symptoms following mTBI. Confounders for the adjusted models will include age, gender, anxiety at baseline, history of migraine, cardiovascular fitness, the presence or absence of neurologic findings, and site of enrolment.
 
The survival probability will be compared using Kaplan-Meier (log rank test) analyses between the 2 treatment arms. Cox proportional hazards regression models will be used to evaluate the differences in time to symptom resolution. Adjusted treatment effects will be estimated in Cox proportional hazards regression models, controlling for the variables listed above. To identify that our randomization strategy was effective, analysis of variance will be used to assess for group-wise differences in age, days since injury to initial visit, initial PCSS score, resting heart rate (HR), and ΔHR during the BCBT and resting BP and ΔBP during the ice bucket test on Day 1. Non-parametric tests of medians will be used to compare the non-normally distributed variable duration of clinical recovery. Chi-

	
squared tests will be used to assess group-wise differences in gender, history of concussions, and incidence of persistent post-concussive symptoms.
 
Safety Analysis
 
Incidence, severity, relationship of treatment emergent adverse events will be presented by treatment group. All vital signs measurements will be summarized at each protocol scheduled time point by treatment group, using either summary statistics or frequency tabulations, as applicable to the type of data. Given the cardiovascular exclusion criteria, ECG data is redundant, and will not be collected.
 
Efficacy Analysis
 
Biomarkers will be summarized at each protocol scheduled time point by treatment group, using either summary statistics or frequency tabulations, as applicable to the type of data. Changes from baseline will also be presented where applicable.
 
Neuropsychology testing will be assessed using the patient reported outcomes and will be summarized at each protocol scheduled time point by treatment group, using either summary statistics or frequency tabulations, as applicable to the type of data. Changes from baseline will also be presented where applicable.
 
Results of the cold pressor test, whiplash test and BCBT will be summarized at each protocol scheduled time point by treatment group, using either summary statistics or frequency tabulations, as applicable to the type of data. Changes from baseline will also be presented where applicable.

--	--

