Accurately identifying the true incidence and duration of ongoing symptoms following concussion has remained elusive, with no reliable way to confirm that symptomatic recovery coincides with brain physiologic recovery.⁹ The diagnosis of concussion relies on self-reported symptoms, which are prone to both over-reporting (e.g., in anxious individuals and malingerers⁵); and under-reporting (e.g., in both athletes and members of the military⁸). An estimated 20% of individuals have persistent post-concussive symptoms (PPCS), as defined by symptoms lasting 2 or more weeks in adults, and 4 or more weeks in adolescents.¹⁰ The 2 best validated instruments for assessing symptom persistence are the Post-Concussion Symptom Inventory (validated in youth from age 5 to 18 years of age¹¹) and the Post-Concussion Symptom Scale (PCSS) (validated in adults¹² and in 13 to 22 year olds¹³). Four distinct symptom clusters: cognitive-fatigue-migraine, affective, somatic, and sleep have been identified as being affected following a concussion.¹³ The presence of pre-existing neuropsychological conditions, especially anxiety, as well as a lack of resilience, have been implicated as contributing to PPCS. Other factors contributing to the severity and duration of post-concussive symptoms have been identified including sex, age, extent of athleticism, history of prior concussions, as well as a history of migraine headaches. Consistent with the objectives of this clinical trial, symptoms of autonomic dysfunction, including exercise-induced headaches, are amongst most prevalent during the first week post-injury, and have also been reported to be the most persistent following mTBI.⁵

Autonomic dysfunction in the form of impaired cerebral autoregulation is commonly seen following mTBI.¹⁵ Standard clinical evaluations are able to assess the integrity of eye movement, balance, and neck function¹⁴, however, there is no easy way to assess autonomic

function in clinical settings. Options for diagnosing autonomic dysfunction following concussion include the Buffalo Concussion Treadmill Test (BCTT);¹⁶ a test performed within a week of injury that has the ability to predict prolonged recovery in concussed adolescents with a sensitivity of 73% and a specificity of 78%.¹⁷ and the “ice bucket test” (also known as the cold pressor test);¹⁸ a simpler and faster way to diagnose autonomic dysfunction following mTBI¹⁹.

[figure not shown]

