4 STUDY DESIGN AND ENDPOINTS

4.1 Description of the Study Design

This study is designed as an open label study of a therapeutic intervention in subjects who have sustained mTBI. At least 400 subjects aged 14 to 45 inclusive will be enrolled in this study at up to 5 study sites. Subjects will be randomly assigned with a ratio of 1:1 to complete either graded exercise or passive stretching. The study sites will have well-established concussion research programs and referral populations.

The therapeutic intervention is either 20 minutes daily of graded exercise or 20 minutes daily of passive stretching delivered through the ClearPlay© mobile application, downloaded to an Apple i-touch or i-phone device, used in conjunction with a wrist-worn heart rate monitoring device (Waveband®). The sponsor will provide one i-touch or i-phone to each subject to provide them with access to ClearPlay App. This device will also allow subjects to access music for use during exercise or stretching.

Randomization of each subject will occur when the subject has completed all of their Baseline physiologic testing (Ice Bucket Test, ClearHeart© and BCBT) on Day 0.

[figure not shown]
Both the site staff treating subjects and the subjects themselves will be aware of the assigned exercise regimen. Subjects will be stratified based on baseline scores on the PCSS (threshold ≥ 30).

The study consists of 2 study visits and 3 remote telephone visits between the 2 study visits:

- Study Visit 1 (Day 0) – Screening/Baseline visit: within 3 to 14 days of concussion. This visit will serve as a screening visit, to determine eligibility to participate in the study. Eligible subjects will be enrolled, and baseline assessments performed;
- Remote telephone safety assessments – Day 14, Day 28 and Day 42 for safety follow up;
- Study Visit 2 – Follow-up visit: 8 weeks following enrolment (Day 56).

A schematic diagram of the study design is presented in Figure 2.

Figure 2: Study Design

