9.6 Efficacy Analysis

The full presentation of the analysis of efficacy data will be presented in the SAP.

For all subjects, daily reported PCSS scores collected from ClearPlay© mobile application will be utilized to determine the resolution of symptoms. The resolution of symptoms is defined as a symptom-severity score of less than each subject's pre-injury PCSS score for 3 consecutive days. To assess differences in the probability of symptom resolution between graded exercise and passive stretching during the 8 weeks of therapy, both unadjusted and adjusted logistic regression models will be used. The primary outcome of the study will be to confirm or refute the superiority of sub-threshold aerobic exercise versus passive stretching to result in resolution of symptoms following mTBI. Confounders for the adjusted models will include age, gender, anxiety at baseline, history of migraine, cardiovascular fitness, the presence or absence of neurologic findings, and site of enrollment.

The survival probability will be compared using Kaplan-Meier (log rank test) analyses between the 2 treatment arms. Cox proportional hazards regression models will be used to evaluate the differences in time to symptom resolution. Adjusted treatment effects will be estimated in Cox proportional hazards regression models, controlling for the variables listed above. To identify that our randomization strategy was effective, analysis of variance will be used to assess for group-wise differences in age, days since injury to initial visit, initial PCSS score, resting HR, and Δ HR during the BCBT and resting BP and Δ BP during the ice bucket test on Day 1. Non-parametric tests of medians will be used to compare the non-normally distributed variable duration of clinical recovery. Chi-squared tests will be used to assess group-wise differences in gender, history of concussions, and incidence of PPCS.

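### The covariate list for the adjusted logistic and Cox models omits days since injury and prior concussion; this costs a little precision but does not bias the comparison

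*Protocol*

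**What the plan says.** Section 9.6 and the synopsis give the same list for the adjusted models. It begins "Confounders for the adjusted models will include age, gender, anxiety at baseline, history of migraine, cardiovascular fitness, the presence or absence of neurologic findings" and ends "cardiovascular fitness, the presence or absence of neurologic findings, and site of enrollment". The Cox models take it over unchanged: "Adjusted treatment effects will be estimated in Cox proportional hazards regression models, controlling for the variables listed above".

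Both omitted variables appear later in the same paragraph, in a different role. An analysis of variance, meant to show that randomisation worked, looks at "group-wise differences in age, days since injury to initial visit, initial PCSS score" and some physiological measures. A chi-squared test compares history of concussions between arms. Neither variable enters a model that estimates the treatment effect.

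Three other places bear on this:

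- Inclusion criterion 3 requires a concussion "diagnosed by a health care professional within 3 to 14 days of enrolment", and section 4.1 sets the first visit accordingly: "Screening/Baseline visit: within 3 to 14 days of concussion". The note to the criterion also requires new or worsened symptoms at enrolment.
- Section 2.1 names factors contributing to the severity and duration of symptoms, "including sex, age, extent of athleticism, history of prior concussions, as well as a history of migraine headaches".
- Table 1 runs the primary Kaplan-Meier analysis on days since concussion. Sections 4.3 and 6.3.2 stratify randomisation by site and by baseline PCSS (<30 or ≥30). Site is in the covariate list and the PCSS stratum is not.

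**The concern.** Entry day should predict outcome in this design. People who recover quickly are no longer eligible late in the window, so those who enter on day 14 are a slower-recovering group than those who enter on day 3. Randomisation is not stratified on entry day, and none of the listed covariates records it.

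Prior concussion is the only factor in the section 2.1 sentence with no counterpart in the model. Sex, age, athleticism and migraine are all there in some form, and no reason is given for leaving the fifth out.

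Three things are at stake, all modest. Omitting a prognostic covariate loses some precision, moves a conditional odds ratio or hazard ratio slightly toward the null, and leaves any chance imbalance between arms in the estimate. Testing the imbalance does not remove it.

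**Working it through.** **Planning figure.** Inputs from section 9.1: 80% and 93% resolution, 90% power, α = 0.05 (taken as two-sided).

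Per arm, n = [1.96·√(2·0.865·0.135) + 1.2816·√(0.8·0.2 + 0.93·0.07)]² / 0.13² = 143.1. The continuity correction gives (143.1/4)·[1 + √(1 + 4/(143.1·0.13))]² = 158.1, or 159 rounded up. The total is 318, against the stated 316. The figure reproduces and does not depend on covariates. Below I use 340 evaluable subjects (400 × 0.85).

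**Is entry day prognostic?** The protocol gives no recovery curve, so this step rests on an assumption: recovery rates vary between people, with S(t) = (1 + t/s)^(−k) for time t since injury. The curve is calibrated to section 2.1's estimate of 20% with persistent symptoms, at 2 weeks (adults) or 4 weeks (adolescents). Then s = T/(0.2^(−1/k) − 1), and the risk of being unresolved 56 days after entry on day d is ((s+d)/(s+d+56))^k. The slope column is the change in log odds of resolution from day 3 to day 14, divided by 11.

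| 20% unresolved at T | k | Entry day 3 | Entry day 14 | Ratio | Slope per day |
|---|---|---|---|---|---|
| 14 days | 0.8 | 13.8% | 30.2% | 2.2 | −0.090 |
| 14 days | 1.0 | 10.4% | 23.8% | 2.3 | −0.090 |
| 14 days | 1.5 | 6.1% | 14.4% | 2.4 | −0.087 |
| 28 days | 1.0 | 15.2% | 27.3% | 1.8 | −0.067 |
| 28 days | 1.5 | 11.7% | 19.6% | 1.7 | −0.055 |

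For k = 1, entry at mid-window (day 8.5) gives (3.5+8.5)/(3.5+64.5) = 18% and (7+8.5)/(7+64.5) = 22%. These bracket the 20% non-resolution that section 9.1 assumes for stretching, so the calibration is plausible.

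**Cox model, time from entry.** Simulation of 340 subjects, entry uniform on days 3 to 14, hazard ratio 1.4 given entry day:

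- Power is 79.6–83.5% without entry day and 80.5–85.2% with it, a gain of about 1 to 3 points.
- Attenuation of the log hazard ratio without it is 1 to 3%.
- The entry-day coefficient is about −0.03 to −0.055 per day.

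**Chance imbalance.** The SD of a uniform entry day on 3 to 14 is √(143/12) = 3.45 days. With 170 per arm, the SE of the difference in means is 3.45·√(2/170) = 0.37 day, so 2 SE is about 0.75 day.

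- Cox: 0.75 × 0.03 to 0.055 shifts the log hazard ratio by 0.02 to 0.04, against a standard error of about 0.12.
- Logistic: 0.75 × 0.055 to 0.090 shifts the log odds ratio by 0.04 to 0.07, against a planned effect of ln(0.93/0.07) − ln(0.80/0.20) = 1.20.

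**Cox model, time from concussion.** A resolution seen in daily app scores needs three days after entry, so the earliest is about day 6 for a day-3 entrant and day 17 for a day-14 entrant. If everyone is counted at risk from injury, the entry-day coefficient is about −0.08 to −0.10 per day. If subjects join the risk set at enrolment (delayed entry), it is near zero (0.006 to 0.010, SE 0.022), and adding it moves the treatment log hazard ratio by at most 0.0015.

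**Logistic model.** Simulation of 340 subjects, 80% v 93%. The 30% with prior concussion and the odds ratios for non-resolution are assumptions.

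| OR per SD of entry day | OR for prior concussion | Power without | Power with | Median log OR without | With | Conditional truth |
|---|---|---|---|---|---|---|
| 1.0 | 1.0 | 94.9% | 94.9% | 1.217 | 1.231 | 1.200 |
| 1.3 | 1.5 | 94.5% | 94.5% | 1.209 | 1.223 | 1.214 |
| 1.7 | 2.0 | 95.1% | 95.8% | 1.217 | 1.279 | 1.252 |
| 2.5 | 3.0 | 94.7% | 97.0% | 1.199 | 1.366 | 1.345 |

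Type I error was 4.9–6.2% without the covariates and 5.0–6.1% with them. The slopes in the first table equal odds ratios of exp(0.055 × 3.45) = 1.2 to exp(0.090 × 3.45) = 1.4 per SD. For entry day alone, the second row is therefore the nearest, and the gain there is nil. A visible gain needs stronger covariates.

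**The case against.** The strongest case against is that this is a preferred covariate set, not an error. Most of its parts stand:

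- **Randomisation protects the comparison.** A reader might infer that the omission biases the treatment effect or makes the test anti-conservative. It does neither. The ordinary standard error already covers chance imbalance, and an unadjusted odds ratio nearer the null is a different estimand, not a mistake. The log-rank test and the unadjusted logistic model do not use the list at all.
- **The clock matters.** With time counted from concussion and delayed entry, adding entry day to the Cox model achieves nothing. This narrows the point but does not remove it: the protocol does not state delayed entry, and the logistic model is unaffected by the choice of clock.
- **Prior concussion is not quantified.** Section 2.1 says it contributes; reading that as driving duration goes beyond the text. Exclusion criterion 1 removes concussions in the last 3 months and head injuries in the last 12 months with residual symptoms, which narrows the factor further.
- **Table 1 adds little.** A reader might infer that its secondary endpoint on recovery by history of injury cannot be estimated. That endpoint need not come from these adjusted models, and the phrase may refer to the index injury.
- **The list may not be closed.** The wording does not bar additions, and 9.6 leaves the full presentation of efficacy analyses to the SAP. But the Cox sentence treats the list as the working set, and 9.2 has the SAP follow the protocol's principal features. The protocol has made a choice here.

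One defence does not hold. Section 6.3.2 presents baseline PCSS as a composite of many pre-existing factors, but baseline PCSS is itself missing from the list and so cannot stand in for the omitted variables.

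**Conclusion.** The point holds as a modest matter of efficiency and coherence. The stated list leaves out entry day, which the design makes prognostic for 8-week resolution and, unless delayed entry is used on the days-since-concussion clock, for time to resolution. It also leaves out prior concussion, which the protocol itself names as a contributor.

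The cost is at most a few power points, a slight attenuation of conditional ratios, and a shift of roughly 0.2 to 0.35 standard errors in the Cox log hazard ratio after an unlucky 2-SE imbalance in entry day. These sizes rest on the assumed recovery curve, uniform entry over days 3 to 14, 340 evaluable subjects, a hazard ratio of 1.4 given entry day and, for the logistic model, assumed odds ratios. The protocol does not support a claim of bias, inflated type I error or an inadequate sample size.

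**What to change.** In 9.6 and the synopsis, add three terms to the pre-specified covariates of the adjusted logistic and Cox models:

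- days from injury to randomisation (continuous);
- history of prior concussion (yes/no);
- baseline PCSS stratum (<30 or ≥30), which randomisation already uses.

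If the time axis stays days since concussion, also state that each subject enters the risk set at the enrolment day. A covariate alone does not handle delayed entry.

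All three variables are already collected, so the cost is one or two sentences in each place and in the SAP. The drawback is a fuller logistic model with few non-resolved subjects. At the planning rates, 340 evaluable subjects give 170 × 0.20 + 170 × 0.07 ≈ 46. Counting one coefficient for treatment, one for each listed covariate other than site, and four for five sites, the model has 11 coefficients and would have 14. That is about 4.2 falling to 3.3 non-resolved subjects per coefficient. The Cox model, where resolution is the event, has far more events and is much less affected.
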